## 8.1 Primary Efficacy Analysis

### *Schiff Sensitivity Score (Day 3)*

The change from baseline (day 0, pre-treatment) in Schiff sensitivity score after 3 days use will be the primary efficacy variable. For each subject, this variable is calculated as the mean change from baseline of the two selected teeth.

Raw Schiff sensitivity scores (raw values averaged over the two test teeth) at day 3 together with changes from baseline (day 0, pre-treatment application) will be summarized by treatment at each study time point. The summary table will display the 'Overall' summary statistics for the baseline (day 0, pre-treatment application) data only. To visually inspect the treatment effect on Schiff sensitivity scores, a plot across time, with the raw means together with standard error bars (SEs) will be produced. The plot will display a different symbol line for each treatment group.

The change from baseline in Schiff sensitivity score will be analyzed using analysis of covariance (ANCOVA) with treatment as factor and baseline Schiff sensitivity score as a covariate. Note that since the baseline Schiff sensitivity score will be included as a covariate, the baseline Schiff stratification value will not be included in the model.

The assumption of normality and homogeneity of variance in the ANCOVA model will be investigated. In case of violation of these assumptions the van Elteren test, adjusting for the maximum baseline Schiff Sensitivity scores will be performed and results will be compared with the ANCOVA results. If the inferences from the two analyses are similar then both sets of results will be reported and emphasis will be made on the ANCOVA results. In case of discrepancies between p-values of ANCOVA and van Elteren analysis, inferences will be drawn on the non-parametric analysis.

Document Name	SAP 207212		
Type	Version	Document Identifier	Effective Date
eldo_clinical_doc	2.0; Most-Recent; Effective; CURRENT	090032d580d31f0c	26-Apr-2017 05:42:24
Reason For Issue	Auto Issue		

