### 9.3.2. Primary Analysis

#### 9.3.2.1 Schiff Sensitivity Score following three days of treatment

The change from baseline in Schiff sensitivity score after 3 days use will be the primary efficacy variable. This will be calculated as the subject level mean change (on two teeth) from Baseline (pre-treatment) of the two selected test teeth..

The change from baseline in Schiff sensitivity score will be analysed using analysis of covariance (ANCOVA) with treatment included as a factor and baseline Schiff sensitivity score included as a covariate. Note that since the Baseline Schiff sensitivity score was included as a covariate, the Baseline Schiff stratification value was not included in the model. The adjusted mean for each treatment, and difference between treatments together with their 95% confidence interval and p-value for the between treatments comparison, will be provided. In addition, to assess efficacy within treatments, the adjusted mean change from baseline (with 2-sided 95% CIs) and p-values from the above model will be presented.

The assumption of normality and homogeneity of variance in ANCOVA model will be investigated. Violation of these assumptions may be overcome using suitable transformation or performing a non-parametric test (e.g., the Wilcoxon Rank Sum test).

Document Name	207212 Clinical Protocol		
Type	Version	Document Identifier	Effective Date
eldo controlled	3.0; Most-Recent; Effective; CURRENT	090032d580c0ede6	28-Aug-2016 15:37:31
Reason For Issue	Auto Issue		

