## 4 Sample Size Determination

Change from baseline in Schiff Sensitive Score will be used to evaluate treatment effects with regard to the primary objective. A sufficient number of subjects will be screened in order to ensure that 92 evaluable subjects per group complete the study.

With 92 evaluable subjects per group, it will be possible to detect a mean difference of 0.25 (SD=0.5198) in change from baseline in Schiff sensitive score after day 3 use between treatments 90% power. The estimate of SD was obtained from a review of GSKCH studies [GSKCH Study 205710; GSKCH Study 205697 & GSKCH Study 205084]. The sample size is based on carrying out two-tailed two sample t-test at a 5% significance level and assumes that the group variances are equal.

Therefore, allowing for dropouts approximately 190 subjects will be randomized to ensure approximately 184 subjects (approximately 92 per arm) complete the study.

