## 5.2 Subgroups/Stratification

Subjects will be stratified by maximum baseline Schiff sensitivity score of the two selected test teeth. This will give rise to two strata:

- Schiff Maximum Score = 2
- Schiff Maximum Score = 3

No subgroup or stratified analyses are planned for this study.

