### *Tactile Threshold (Day 0, Post-Treatment and Day 3)*

The change from baseline in tactile threshold to day 3 will be calculated as the mean change from baseline of the two selected test teeth.

Tactile threshold scores (raw values averaged across the two test teeth) together with changes from baseline will be summarized at each time point as described for the Schiff sensitivity score. A plot with raw means and standard error bars for each treatment group across time will be produced to visually inspect the treatment effect on tactile threshold score. The plot will display a different symbol line for each treatment group.

The change from baseline (day 0, pre-treatment) in tactile threshold to day 3 will be analyzed using ANCOVA with treatment and baseline Schiff stratification included as factors and baseline tactile threshold included as a covariate.

The assumption of normality and homogeneity of variance in ANCOVA model will be assessed as described for the primary efficacy analysis.

The change from baseline (day 0, pre-treatment) in tactile threshold to day 0 post-treatment application will be summarised and analysed as described for the changes from baseline in tactile threshold to day 3.

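### The primary Schiff ANCOVA omits the randomisation stratum, which its linear baseline covariate carries only in part; adding it is a small, nearly free gain in precision

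*SAP*

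**What the plan says.** SAP 5.2 states: "Subjects will be stratified by maximum baseline Schiff sensitivity score of the two selected test teeth". This gives two strata, maximum 2 and maximum 3. Protocol 5.8.1 assigns randomisation numbers within each of them.

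The primary model in SAP 8.1 has treatment as the factor and baseline Schiff as the covariate. Because that covariate is present, "the baseline Schiff stratification value will not be included in the model". Protocol 9.3.2.1 gives the same reason and says that "the Baseline Schiff stratification value was not included in the model". The statistical methods in the protocol synopsis describe the same model. SAP 8.2 carries it over to the Day 0 post-treatment Schiff score.

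The stratum is used in two other places. The tactile change is "analyzed using ANCOVA with treatment and baseline Schiff stratification included as factors and baseline tactile threshold included as a covariate" (SAP 8.2). If the assumptions of the Schiff ANCOVA fail, "the van Elteren test, adjusting for the maximum baseline Schiff Sensitivity scores will be performed" (SAP 8.1).

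**The concern.** The reason given for leaving the stratum out is sound only if the baseline covariate already carries it. SAP 8.1 summarises Schiff scores as averages over the two teeth, so the covariate is a mean, while the stratum is defined by a maximum. The mean enters as a straight line, but the stratum is a step.

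If response differs between the strata by more than a straight line can follow, that variation stays in the residual although the randomisation has balanced it. The standard error of the primary comparison is then slightly larger than it need be. What is at stake is precision on the endpoint that alone decides success.

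**Working it through.** **1. The planned sample size.** The inputs are in SAP section 4: "detect a mean difference of 0.25 (SD=0.5198) in change from baseline", a "two-tailed two sample t-test at a 5% significance level", and "between treatments 90% power".
- Normal approximation: n = 2 × (1.960 + 1.282)² × 0.5198² / 0.25² = 90.9, so 91 per arm.
- Exact noncentral t: 89.7% power at 91 per arm and 90.06% at 92. The plan's 92 per arm is reproduced.
- The test has no covariate, and 0.5198 is given as the SD of the change itself. It therefore already contains any variation between strata.

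**2. Possible baseline values.** Protocol 4.1 requires a Schiff score of at least 2 on each test tooth, and the scale ends at 3.

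| Tooth scores | Mean (covariate) | Maximum (stratum) |
|---|---|---|
| 2, 2 | 2.0 | 2 |
| 2, 3 | 2.5 | 3 |
| 3, 3 | 3.0 | 3 |

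The stratum indicator is 0, 1, 1 at 2.0, 2.5, 3.0. No straight line passes through those three points.

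**3. How much of the stratum the line carries.** The documents give no baseline distribution, so the mixes are assumed. Let a, b and c be the proportions at 2.0, 2.5 and 3.0, and code the covariate x = −1, 0, 1. The part of the stratum variance that the line misses is abc / var(x).
- Mix 60/25/15%: var(x) = 0.75 − 0.45² = 0.5475. Missed: 0.0225 / 0.5475 = 0.0411. The stratum variance is 0.6 × 0.4 = 0.24, so R² = 1 − 0.0411/0.24 = 83%.
- Mix 25/50/25%: var(x) = 0.50. Missed: 0.03125 / 0.50 = 0.0625. The stratum variance is 0.25 × 0.75 = 0.1875, so R² = 67%.

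R² depends on the mix. If the chance that a tooth scores 3 runs from 0.1 to 0.9 and the within-subject correlation from 0 to 0.6, R² runs from 18% to 95%. The lowest values arise when almost nobody is in stratum 1, and little variance is then at stake. Over all mixes the missed variance is at most 0.0625, reached at 25/50/25%.

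**4. Size relative to the planned variance.** A step of s Schiff points beyond linear leaves s² × (missed variance) in the residual. This is compared with 0.5198² = 0.2702.

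| Assumed step | 60/25/15% | 25/50/25% |
|---|---|---|
| 0.2 | 0.6% | 0.9% |
| 0.3 | 1.4% | 2.1% |
| 0.4 | 2.4% | 3.7% |

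On this scale the largest entry, 3.7%, raises the standard error by a factor of √1.037 = 1.018.

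**5. Effect on the primary comparison.** Assumptions: 184 subjects, mix 30/40/30%, residual SD 0.5, blocks of 4 within stratum.
- With a 0.4 step, the missed stratum variance is 0.3 × 0.4 × 0.3 / 0.6 = 0.06. Without the stratum, SE = √(0.25 + 0.16 × 0.06) × √(2/92) = 0.0751. With it, SE = 0.5 × √(2/92) = 0.0737. Simulation gave 0.0750 and 0.0737.
- Approximate power for a difference of 0.25 is Φ(0.25/0.0750 − 1.96) = 91.5% without the stratum and Φ(0.25/0.0737 − 1.96) = 92.4% with it, about 1 point more.
- With no step, the simulated SE was 0.0735 without the stratum and 0.0737 with it. Nothing material is lost.

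**6. Validity of the planned model.** Separate simulations used a residual SD of 0.5198, several mixes, and steps up to 1.0. The planned model showed no bias in the treatment difference and a type I error of 4.5% to 5.2%.

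**The case against.** The case for leaving the model alone is substantial, and most of it stands.

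- **The omission is deliberate, reasoned and identical in protocol and SAP.** This stands; the two documents do not conflict. A reader might still infer that the Schiff models ignore the randomisation. They do not: for eligible subjects the stratum is a deterministic function of the baseline mean, which is in the model and also separates 2.5 from 3.0, as the stratum cannot. Only the functional form is at issue.
- **Planned power is untouched.** This stands. Taking 0.5198 as the residual SD and adding a 1.0-point step on top gives 83% to 86% power for the planned model, and a reader might conclude that the trial is underpowered. The documents do not support that. They give 0.5198 as the SD of change for an unadjusted test, nothing in them points to such a step, and 1.0 is large on a 0 to 3 scale.
- **Use of the stratum elsewhere has ordinary explanations.** This stands. The tactile model has no other Schiff term, and the van Elteren test needs discrete strata. One might expect the fix to align the ANCOVA with van Elteren. It would not: the ANCOVA would then distinguish three baseline levels and van Elteren still two.
- **Three baseline values hold only for eligible subjects.** This stands. The ITT definition does not remove subjects who breached an entry criterion, so the step-2 table and the equivalence to a three-level factor are conditional.

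What remains is that the stated reason for the exclusion is only partly true, and that including the stratum costs almost nothing.

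**Conclusion.** The concern holds as a minor improvement to the primary and single-use Schiff models. The linear baseline term carries the randomisation stratum only in part, about 67% to 83% under the assumed mixes. There is no bias, no inflation of type I error and no loss of the planned 90% power. The precision forgone is about 1 power point for an assumed 0.4-point step beyond linear, and zero if the relation is linear.

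This rests on four assumptions: the covariate is the two-tooth mean, as SAP 8.1 implies (if it were the maximum it would equal the stratum); analysed subjects met the entry criteria; the baseline mix lies in the range shown; and any step is of the size assumed. The documents give neither the mix nor the step, nor the block size used in the simulations.

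**What to change.** - In SAP 8.1, and through it the Day 0 Schiff analysis in SAP 8.2, fit treatment and the randomisation stratum (maximum Schiff 2 / 3) as factors, with baseline Schiff as covariate. State that the covariate is the two-tooth mean. For eligible subjects, when all three baseline values occur, this is the same model as baseline Schiff as a three-level factor, so it also removes the linearity assumption.
- Delete the sentence in SAP 8.1 that excludes the stratum.
- Update footnote [2] of Table 9.3.1.2 and footnote [1] of the in-text efficacy table in SAP section 11.
- Before unblinding, record the departure from Protocol 9.3.2.1 and from the synopsis in SAP section 12, which now reports no changes. Without this entry the edit would create a protocol-SAP conflict on the primary model.

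The cost is this wording, one model term and one of about 181 residual degrees of freedom (184 subjects less 3 parameters). No new data are needed and the sample size does not change.

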## 8.2 Secondary Efficacy Analysis

### *Schiff Sensitivity Score (Day 0, Post-Treatment)*

The change from baseline (day 0, pre-treatment application) in Schiff sensitivity score to post-treatment application (day 0, post-treatment application) will be summarised and analysed as detailed for the primary endpoint. Analysis assumptions will be investigated as detailed for the primary efficacy analysis.

### *Tactile Threshold (Day 0, Post-Treatment and Day 3)*

The change from baseline in tactile threshold to day 3 will be calculated as the mean change from baseline of the two selected test teeth.

Tactile threshold scores (raw values averaged across the two test teeth) together with changes from baseline will be summarized at each time point as described for the Schiff sensitivity score. A plot with raw means and standard error bars for each treatment group across time will be produced to visually inspect the treatment effect on tactile threshold score. The plot will display a different symbol line for each treatment group.

The change from baseline (day 0, pre-treatment) in tactile threshold to day 3 will be analyzed using ANCOVA with treatment and baseline Schiff stratification included as factors and baseline tactile threshold included as a covariate.

The assumption of normality and homogeneity of variance in ANCOVA model will be assessed as described for the primary efficacy analysis.

The change from baseline (day 0, pre-treatment) in tactile threshold to day 0 post-treatment application will be summarised and analysed as described for the changes from baseline in tactile threshold to day 3.

## 8.3 Other Efficacy Analysis

Not applicable.

## 9 Safety Analysis

Safety population will be used for safety assessments. Safety analyses will be performed according to the treatment that the subject received (using variable ATRT).

Document Name	SAP 207212		
Type	Version	Document Identifier	Effective Date
elido_clinical_doc	2.0; Most-Recent; Effective; CURRENT	090032d580d31f0c	26-Apr-2017 05:42:24
Reason For Issue	Auto Issue		

No inferential analysis will be performed to compare treatments with respect to safety.

All adverse events (AEs) will be reviewed by the Clinical Research Scientist or Designee prior to database lock and unblinding and will be coded using the Medical Dictionary for Regulatory Activities (MedDRA). During this review stage, AEs will be further categorized as oral or non-oral. AEs will be listed and summarized by treatment received. Serious AEs will also be listed. AEs will be regarded as treatment emergent if they occur on or after the first treatment application at the baseline visit.

The following AEs tables split by treatment will be produced:

- Listing of all AEs (including Non-treatment emergent AEs from all subjects)
- Listing of all AEs for screened subjects
- Treatment emergent AEs by Oral/Non-Oral Preferred Term (PT)
- Treatment emergent AEs by System Organ Class (SOC) and PT
- Treatment emergent treatment related AEs by Oral/Non-Oral
- Listing of serious AEs (if there are none a null listing will be produced; if there are more than 5 treatment emergent serious AEs (SAEs) a table will be produced instead by SOC and PT)
- Non-serious treatment emergent AEs by SOC and PT (only produced if there are more than 5 SAEs).
- Listing of incidents (if there is none a null listing will be produced).

Oral soft tissue (OST) abnormalities will be listed only.

## 10 Interim Analysis

No interim analyses are planned for this study.

Document Name	SAP 207212		
Type	Version	Document Identifier	Effective Date
eldo_clinical_doc	2.0; Most-Recent; Effective; CURRENT	090032d580d31f0c	26-Apr-2017 05:42:24
Reason For Issue	Auto Issue		

## 11 Topline Summary

### 11.1 Variables for topline

#### *Efficacy*

Efficacy variable 1 (Change from baseline in Schiff sensitivity score after a single 60 second direct application and 3 days use)

Efficacy variable 2 (Change from baseline in Tactile score after a single 60 second direct application and 3 days use)

#### *Safety*

Adverse events

Incidents

### 11.2 Outputs for topline

Datasets/Tables	Description
Datasets	PONNFL, POPNEXCL, RANDOM  ADSL, ADAE, ADXXXX, ADXXXX, INCIDENT, S_DH_W and S_DH_B
Tables Safety	9.4.1 – Listing of Adverse Events – Safety Population  9.4.2 – Treatment Emergent Adverse Events, Oral and Non-Oral by Preferred Term - Safety Population
Tables Efficacy (In-text table)	Statistical Analysis of Change from Baseline in Evaporative (Air) Sensitivity – Schiff Sensitivity Score.  Statistical Analysis of Change from Baseline in Tactile Sensitivity – Tactile Threshold (g) - Intent to Treat Population.
Figures (Excel plot)	9.3.1 – Evaporative (Air) Sensitivity - Schiff Sensitivity Score by Time and Treatment Group -

Document Name	SAP 207212		
Type	Version	Document Identifier	Effective Date
eldo_clinical_doc	2.0; Most-Recent; Effective; CURRENT	090032d580d31f0c	26-Apr-2017 05:42:24
Reason For Issue	Auto Issue		

Datasets/Tables	Description
	Intent to Treat Population 9.3.2 – Tactile Sensitivity - Tactile Threshold (g) by Time and Treatment Group - Intent to Treat Population
Other output	Table 9.1.1 – Subject Disposition - All Screened Subjects

## In-text table format for efficacy

Statistical Analysis of Change from Baseline in Evaporative (Air) Sensitivity - Schiff Sensitivity Score  
 Intent to Treat Population

Time point	Adjusted Mean Change (95% Confidence Interval), p-value		
	Test Dentifrice (N=XX) [1]	Control Dentifrice (N=XX) [1]	Treatment Comparison: Test Dentifrice vs. Control Dentifrice [2]
Baseline	x.xx (SE= x.xx)	x.xx (SE= x.xx)	
Day 0 (Post treatment)	x.xx (x.xx, x.xx) p= x.XXXX	x.xx (x.xx, x.xx) p= x.XXXX	x.xx (x.xx, x.xx) p= x.XXXX
Day 3	x.xx (x.xx, x.xx) p= x.XXXX	x.xx (x.xx, x.xx) p= x.XXXX	x.xx (x.xx, x.xx) p= x.XXXX

Note: Baseline values are Raw Means with SE included in brackets.

[1] Adjusted mean change, CI and p-value from ANCOVA model with treatment as factor and baseline Schiff score as covariate.

[2] Negative difference favours Test dentifrice.

Note to programmer: 1) Please create these tables in docs. Format  
 2) For tactile analysis footnote 1 & 2 will be changed to

[1] Adjusted mean change, CI and p-value from ANCOVA model with treatment and Schiff strata as factors and baseline Tactile score as covariate.

[2] Positive difference favours Test dentifrice.

3) If Non parametric methods used for analysis in-text table format and footnote will be changed and these will be provided by the statistician.

## 12 Changes to Planned Analysis

There are no planned changes from the analyses planned in the protocol.

Document Name	SAP 207212		
Type	Version	Document Identifier	Effective Date
eldo_clinical_doc	2.0; Most-Recent; Effective; CURRENT	090032d580d31f0c	26-Apr-2017 05:42:24
Reason For Issue	Auto Issue		

## Appendix 1 Study Schedule

Procedure/ Assessment	Visit 1	Visit 2		Visit 3
	Screening	Day 0 Baseline (Pre-Treatment)	Day 0 Post-Treatment	Day 3
Informed consent	X			
Demographics and Medical History	X			
Current / Concomitant medication	X	X		X
Inclusion / Exclusion Criteria	X	X 		
Subject Eligibility	X	X		X
Continuation Criteria		X		X
Oral Soft Tissue (OST) Examination	X	X	X	X
Oral Hard Tissue Examination including Eligible Teeth Assessments (Dentition Exclusions, EAR, MGI, Tooth Mobility)	X			
Qualifying Evaporative Air Sensitivity Assessment (Y/N)	X			
Dispense Acclimatisation Toothpaste, Toothbrush, Timer	X			
Supervised Brushing with Acclimatisation Toothpaste	X			
Return Acclimatisation Toothpaste, Toothbrush		X		
Compliance Check		X 		X 
Tactile Sensitivity Assessment (Yeaple Probe)		X 		
Evaporative Air Sensitivity Assessments (Schiff sensitivity score)		X 		
Selection of two 'Test Teeth'		X 		
Stratification/Randomisation		X		
Dispense Study Supplies		X 		
Supervised direct application of allocated dentifrice (Test Teeth Only)		X 		
Tactile and Evaporative Air Assessments  (Test Teeth only)			X	X
Supervised Brushing			X 	
Return Study Supplies				X
Adverse Events / Incidents 	X	X	X	X

Acclimatisation Period (minimum 4 weeks – maximum 8 weeks)

Document Name	SAP 207212		
Type	Version	Document Identifier	Effective Date
eldo_clinical_doc	2.0; Most-Recent; Effective; CURRENT	090032d580d31f0c	26-Apr-2017 05:42:24
Reason For Issue	Auto Issue		

Study Conclusion					X
------------------	--	--	--	--	---

1. Inclusion criteria 5d
2. Subject asked to confirm that they have brushed with the acclimatisation product as directed during the acclimatisation period.
3. To be performed pre treatment on all teeth that meet the dentition exclusions, EAR, MGI and tooth mobility criteria at Screening until the examiner selects 2 teeth meet the study criteria, at which point no further teeth will be tested. Maximum force to be tested will be 20g.
4. To be performed pre-treatment on teeth that meet tactile threshold inclusion criterion (<=20g) at Baseline and should follow the tactile assessment with a minimum of 5 mins between the last tactile assessment and the first evaporative air assessment to allow the teeth recovery time.
5. Tactile assessment to be performed, on the two selected test teeth only. Maximum force to be tested will be 80g. Evaporative air assessment should follow the tactile assessment with a minimum of 5 mins between the last tactile assessment and the first evaporative air assessment to allow the teeth recovery time.
6. Experimental dentifrice, control dentifrice, toothbrush, product usage instructions, and diary. Timer dispensed in Visit 1 will be kept and re used.
7. Based on subject completed diary card
8. To be performed after stratification and randomisation
9. Tactile assessment to be performed, on the two selected test teeth only. Maximum force to be tested will be 80g. Evaporative air assessment should follow the tactile assessment with a minimum of 5 mins between the last tactile assessment and the first evaporative air assessment to allow the teeth recovery time.
10. Supervised whole mouth brushing before leaving the site (after all clinical assessments have been performed)
11. Incidents captured from Visit 2.

Document Name	SAP 207212		
Type	Version	Document Identifier	Effective Date
elido_clinical_doc	2.0; Most-Recent; Effective; CURRENT	090032d580d31f0c	26-Apr-2017 05:42:24
Reason For Issue	Auto Issue		

